1.1.5 Anal HPV and anal intraepithelial neoplasia prevalence among HIV-positive women

Few studies have reported estimates of anal HPV and anal cytology prevalence, and fewer have reported anal histology results.^{27,28,29} Despite the data on cervical HPV infection and cervical disease in HIV-positive women and data on anal HPV, cytologic abnormalities, and histologic abnormalities among HIV-positive men, there are limited data on anal HPV infection and disease among HIV-positive women. There have only been 4 studies describing the prevalence of HPV infection and anal infection among HIV-positive women.²⁷⁻³⁰ In these studies the rates of anal HPV varied dramatically from 16%-90% and the prevalence of anal cytologic abnormalities varied from 17%-39%. The variance in HPV prevalence is likely due to differences in the type of test performed and possibly the transport medium of the test. There are even less data reported regarding anal histologic diagnoses. Among those studies where HRA and biopsy were performed,²⁷⁻²⁸ histology results were only available in a small percentage of their population. Additionally, only one longitudinal study has been published describing incidence of anal HPV infection, and the cohort for this study was recruited in the pre-cART/early cART era.³¹ Therefore, further comprehensive studies in the cART era are needed to determine more precise estimates of factors impacting anal HPV infection, cytologic abnormalities, and anal histologic diagnoses.

There are no data evaluating the screening test characteristics of U.S. Food and Drug Administration (FDA) -approved and experimental HR HPV testing for anal cancer screening among HIV-positive women. Among HIV-positive MSM, it has been shown that HPV testing adds little information to anal cytologic testing because of the very high prevalence of anal HR HPV prevalence (in most populations > 90%).³² However, it appears that HIV-positive women may have a lower rate of anal HR HPV infection; therefore, HR HPV testing may improve the SN and SP of anal cytology. There have been no studies evaluating HR HPV test characteristics among HIV-positive women, using either the FDA-approved Hybrid Capture 2 (HC2) test (Qiagen Corporation, Gaithersburg, MD), the APTIMA HPV test (GenProbe Corp, San Diego, CA), or the OncoE6™ test (Arbor Vita, Fremont, CA), a test that is currently in development.

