1.1.7 APTIMA HPV Test

The APTIMA HPV test detects messenger RNA (mRNA) for HPV proteins E6/E7 in 14 oncogenic HPV types. Of all experimental HPV tests, the APTIMA test has

recently received FDA approval for cervical HPV testing based on studies that have shown the APTIMA test to significantly improve the specificity of detecting CIN2+, thereby decreasing the number of “false positive” HPV tests compared to HC2. The test may be more predictive than the detection of HPV DNA alone because upregulation of mRNA from the oncogene region of the HPV genome (E6 and E7) likely predicts which HPV infections are more likely to persist and progress to a high-grade lesion and cancer. The performance characteristics of APTIMA HPV were compared with HC2 for the detection of CIN2+ in specimens collected from women referred for colposcopy because of abnormal cytology. APTIMA HPV had an SN of 95.2% and an SP of 42.2%, compared with HC2, which had an SN of 99.6% and an SP of 28.4% when used without concurrent cytology.³⁴

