2.0 HYPOTHESIS AND STUDY OBJECTIVES

2.1 Hypotheses

- 2.1.1 Anal HPV testing with HC2, APTIMA, or Arbor Vita OncoE6 HPV Test will improve the performance, including the SN and SP of anal cytology testing among HIV-positive women when measured against the gold standard, biopsy-proven HSIL.
- 2.1.2 Anal HSIL and anal HPV infection are associated with risk factors including cervical HPV, behavioral, and immunologic characteristics, such as plasma HIV RNA, current CD4 and nadir CD4 counts.

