2.2 Primary Objectives

- 2.2.1 To determine the sensitivity and specificity of HPV testing using different methods of detection, including HPV Hybrid Capture 2 (HC2), HPV mRNA assays (APTIMA) and Arbor Vita OncoE6 HPV assay and whether they improve the screening performance of routine anal cytology for the detection of anal HSIL when measured against the gold standard, biopsy-proven HSIL.
- 2.2.2 To determine the prevalence and risk factors for prevalent HSIL in HIV-positive women.
- 2.2.3 To determine incidence and risk factors associated with anal HSIL and HPV over 2 years among HIV positive women undergoing semi-annual anal evaluations.

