7.0 STATISTICAL CONSIDERATIONS

7.1 Sample Size

The primary objective of the study is to evaluate the sensitivity and specificity of the following methods for the detection of HSIL of the anus (as determined by consensus pathology): anal cytology, HPV hybrid capture 2, HPV mRNA assays (APTIMA) and Arbor Vita OncoE6 HPV test. Note that throughout this section, HSIL (of the anus) is defined as the local or consensus pathology interpretation of any anal biopsy. At the initial visit, all women will undergo an HRA-directed biopsy to determine if they have HSIL. Since HRA is considered the “gold standard,” the findings on HRA will determine whether a woman is classified as having HSIL or not. HSIL may be under-diagnosed due to operator error, thus the diagnosis of HSIL will be based on the procurement of at least 2 biopsies during HRA. HSIL will be thus be defined as having the diagnosis determined by either local pathologist or the consensus pathology on *any* anal biopsy at a given visit. Based on previous reports,⁴¹ it is anticipated that approximately 10% of women will have HSIL. The prevalence of HRA-proven HSIL can be estimated with a 95% confidence interval of +/- 3.3%.

For each of the methods of detection, the null hypothesis that the sensitivity is 50% can be tested against the alternative that sensitivity is at least 75% at the one-sided 0.05 significance level with power of 0.89 with 30 HSIL participants. The HPV test results from all three tests—APTIMA, HC2, and HPVE6E7—are all dichotomous, i.e., reported as either positive or negative (or unevaluable). With 270 women who are negative for HSIL on HRA, the null hypothesis that specificity is 50% can be tested against the alternative hypothesis that specificity is at least 65% at the one-sided 0.05 significance level with power of 0.99.

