The novel methods of detection (HPV hybrid capture 2, HPV mRNA assays (APTIMA) and Arbor Vita Onco E6 HPV test) will be evaluated to determine if they improve sensitivity or specificity compared to routine anal cytology using McNemar’s test. With 30 HSIL women, a 20% increase in sensitivity with 25% of participants with discordant results can be detected at the one-sided 0.05 significance level with 78% power. With 270 women negative for HSIL, a 20% increase in specificity with 25% of participants with discordant results can be detected at the one-sided 0.05 significance level with 99% power. Positive and negative predictive values will be assessed for each method of detection.

To determine incidence of HSIL, we will use the information from the women whose initial HRA examination is negative for HSIL. If these women are followed for an average of 1.8 months, we would expect $1.8 \times 270 = 486$ person-years of follow-up. The table below shows the 95% Poisson confidence intervals for two levels of the underlying incidence of HSIL with 486 person-years of observation:

| Underlying incidence of HSIL per 100 person-years | 95% Poisson confidence interval (per 100 person-years) |
|---------------------------------------------------|--------------------------------------------------------|
| 2.06 | (1.11, 3.82) |
| 3.09 | (1.86, 5.12) |

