7.2 Primary Statistical Analyses

7.2.1 Primary analyses

To estimate the sensitivity and specificity of each of the methods of detection, the binomial proportion and its 95% confidence interval will be used. Among participants who are HRA positive for HSIL, McNemar's test will be used to compare routine anal cytology with each of the other methods of detection to determine if sensitivity in the diagnosis of HSIL is improved with the other methods. Similarly, among participants who are HRA negative for HSIL, McNemar's test will be used to compare routine anal cytology with each of the other methods of HPV detection to improve specificity. Positive and negative predictive values will be estimated for each method of detection.

The prevalence of HSIL will be estimated as the proportion of women who are HRA positive for HSIL at entry and its 95% confidence interval. Logistic regression analyses will be used to evaluate the association of potential risk factors (cervical HPV, abnormal cervical cytology, behavioral, and immunologic characteristics, such as plasma HIV-1 RNA, current and nadir CD4 count) with diagnosis of HSIL.

To estimate the incidence of HSIL among women who were HRA negative for HSIL at study entry, the Poisson rate and its 95% confidence interval will be estimated from the number of HSIL cases detected divided by the cumulative years of follow-up across these cases. Behavioral risk factors will be assessed by research staff administered surveys at each study visit. Included in these risk factors is the risk of ongoing sexual exposure to HPV in the study population. Logistic regression will be used to evaluate potential risk factors for incidence of HSIL.

To estimate the incidence of anal HPV among women who were negative for anal HPV at study entry, the Poisson rate and its 95% confidence interval will be estimated from the number of anal HPV cases detected divided by the cumulative years of follow-up across these cases. Logistic regression will be used to evaluate potential risk factors for incidence of anal HPV.

Analysis of the results of the Arbor Vita assay will be delayed after the primary analysis is performed using the results of the Hybrid Capture 2 and Aptima Assays, if the Arbor Vita assay is optimized to yield sufficient results from anal cytology specimens in the future.

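### Section 7 tests each HPV assay alone against cytology alone; it plans no confidence interval for the paired difference and no estimate of cytology and HPV used together

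*Combined protocol and SAP*

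**What the plan says.** Objective 2.2.1 asks for the accuracy of each HPV assay and "whether they improve the screening performance of routine anal cytology for the detection of anal HSIL". Hypothesis 2.1.1 expects that HPV testing "will improve the performance, including the SN and SP of anal cytology testing among HIV-positive women". Section 1.1.5 gives the motive: in HIV-positive MSM, "HPV testing adds little information to anal cytologic testing" because high-risk HPV is so common, whereas women may have a lower rate; "therefore, HR HPV testing may improve the SN and SP of anal cytology".

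Section 7.1 restates the primary objective as to "evaluate the sensitivity and specificity of the following methods for the detection of HSIL of the anus", and lists cytology and the three HPV assays as separate methods. The HPV methods "will be evaluated to determine if they improve sensitivity or specificity compared to routine anal cytology", by McNemar's test. Section 7.2.1 uses that test "to compare routine anal cytology with each of the other methods of detection to determine if sensitivity in the diagnosis of HSIL is improved" among women with HSIL, and does the same for specificity among women without it.

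The other planned outputs are a sensitivity and a specificity with a binomial 95% CI for each method, and predictive values for each method. Neither section defines a combined anal cytology-plus-HPV result, plans an interval for a paired difference, or says that the paired tables will be shown.

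**The concern.** Two different questions fit the wording of the objective. One is replacement: is an HPV assay on its own better than cytology on its own? The other is added value: what is gained, and at what cost, when HPV testing is used with cytology? Section 7 addresses the first. Hypothesis 2.1.1, objective 2.2.1 and section 1.1.5 describe cytology itself as the thing improved, which also fits the second.

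If the second question is of interest, readers would learn how each assay compares with cytology, but not how many more HSIL cases the pair finds or how many more women are falsely positive. Even for the first question, McNemar's test gives a p-value, and two separate binomial intervals do not make an interval for the difference between paired results. With about 30 HSIL cases, the width of that interval matters to anyone reading the result.

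**Working it through.** **Inputs from 7.1.** 30 women with HSIL and 270 without (10% of 300). McNemar comparison: a 20-point gain with 25% discordant, one-sided 0.05. Alternative values for a single method: sensitivity 75%, specificity 65%.

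**1. The plan's own power.** Write b for the proportion where the HPV assay is right and cytology wrong, and c for the reverse. From b - c = 0.20 and b + c = 0.25, b = 0.225 and c = 0.025. With n = 30, d = 0.20, psi = 0.25 and z = 1.645:

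- Miettinen's approximation: (d*sqrt(n*psi) - z*psi) / sqrt(psi^2 - d^2*(3 + psi)/4) = (0.548 - 0.411)/0.173 = 0.788, so power is 78.5%.
- Full enumeration of the uncorrected asymptotic test: 77.6%.

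Both agree with the stated 78%. With n = 270, power exceeds 99.9%, consistent with the stated 99%. These figures apply to assay alone versus cytology alone.

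**2. The interval that is not planned.** Wald half-width = 1.96*sqrt((psi - d^2)/n).

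- Sensitivity, n = 30: 1.96*sqrt(0.21/30) = 0.164, so +20 points (3.6 to 36.4).
- Specificity, n = 270: 1.96*sqrt(0.21/270) = 0.055, so +20 points (14.5 to 25.5).
- If discordance were 47.5% (assumed: 75% versus 55%, independent), n = 30: 1.96*sqrt(0.435/30) = 0.236.

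**3. Why single-method results do not fix combined accuracy.** Assume cytology and the assay are both 75%/65%. The paired difference is zero on both measures, and McNemar's statistic is zero whatever the overlap.

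| Assumed overlap | Either positive (sens/spec) | Both positive (sens/spec) |
|---|---|---|
| Full | 75% / 65% | 75% / 65% |
| 25% discordant, equal split | 87.5% / 52.5% | 62.5% / 77.5% |
| Conditional independence | 93.75% / 42.25% | 56.25% / 87.75% |
| Least possible | 100% / 30% | 50% / 100% |

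The equal split moves each figure by 0.125. Independence moves sensitivity by 0.75*0.25 = 0.1875 and specificity by 0.65*0.35 = 0.2275. At least overlap, either-positive specificity is 2*0.65 - 1 = 0.30 and both-positive sensitivity is 2*0.75 - 1 = 0.50. In counts, either-positive in the two middle rows finds 0.125*30 = 3.75 to 0.1875*30 = 5.6 more HSIL, for 0.125*270 = 33.75 to 0.2275*270 = 61.4 more false positives.

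**4. The same check with 7.1's cells.** Apply b = 0.225 and c = 0.025 to both measures at once (an assumption). Against cytology alone:

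- Either positive: +0.225*30 = 6.75 HSIL and +0.025*270 = 6.75 false positives.
- Both positive: -0.025*30 = -0.75 HSIL and -0.225*270 = -60.75 false positives.

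**5. Precision of the either-positive gain.** The gain is a single cell p, with half-width 1.96*sqrt(p(1-p)/n). For n = 30: 0.118 (p = 0.125), 0.140 (0.1875), 0.149 (0.225). For the specificity loss with n = 270: 0.039 (0.125) and 0.050 (0.2275). Exact 95% CIs for the gain: 4/30, 3.8% to 30.7%; 6/30, 7.7% to 38.6%.

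**The case against.** The strongest reply is that section 7 has already settled the meaning: improvement is judged in comparison with cytology, method against method. Sections 1.1.11 and 1.2 support this by speaking of the characteristics of the individual tests, and 1.1.7 cites assay accuracy "when used without concurrent cytology". Hypothesis 2.1.1 names both sensitivity and specificity. An either-positive rule cannot raise specificity and a both-positive rule cannot raise sensitivity, so neither simple rule could meet that hypothesis, whereas an assay on its own could. This stands. It is why the combined-result gap is conditional on the added-value reading, and why the combinations belong as descriptive estimates.

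A second reply is that the information is nearly there. McNemar's test is computed from the discordant cells, which with the single-method results give both combination rules exactly when every woman has both results. When the two tests differ, the discordant total might even be worked back from an unrounded p-value. This also stands, but it describes what the data contain. The plan does not commit to showing the cells, 7.1 allows for unevaluable results, and when the two tests perform alike the p-value carries nothing about overlap.

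A third reply is that the added sensitivity estimates are imprecise. They are, and the interval lets a reader see that.

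A reader might go further and infer that the McNemar tests or their power are wrong, or that the first primary objective has no analysis. The documents do not support that: the tests answer the comparison that section 7 sets, and the powers reproduce.

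**Conclusion.** The planned tests should stay. The gap has two parts of different strength. The absence of a confidence interval for the paired difference holds on either reading; at 7.1's design values that interval is about +/-16 points for sensitivity and +/-5.5 for specificity. The absence of any combined cytology-plus-HPV estimate matters if added value is part of the objective, a reading that 2.1.1, 2.2.1 and 1.1.5 support but section 7 does not adopt.

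The 75%/65% examples rest on assumed accuracy and overlap. The documents give no expected accuracy for cytology in this population, and 7.1 does not say its discordance applies to both measures together. The figures show that overlap decides the answer; they are not forecasts of gain or harm. This is a worthwhile, low-cost improvement to the analysis plan. The design and data collection need no change.

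**What to change.** Keep the McNemar tests and their stated power. In 7.2.1, state whether improvement means replacing cytology, adding to it, or both. For HC2 and APTIMA (OncoE6 if it is analysed later), among women with both results evaluable and at a stated cytology cut-off (for example the normal/abnormal split that 8.4 uses for site monitoring), add:

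1. The paired difference in sensitivity and in specificity, assay minus cytology, each with a 95% CI, and the paired 2x2 tables by HSIL status. Name an interval method suited to paired data with about 30 cases.
2. As descriptive secondary estimates, the sensitivity and specificity of *cytology or HPV positive* and *cytology and HPV positive*, with their paired differences from cytology alone and 95% CIs. Show the two measures side by side as a trade-off, without significance tests, because neither rule can improve both.

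**Cost.** SAP text only; the swabs are already collected at the same visits. The plan gains 2 assays x 3 comparisons x 2 measures = 12 paired differences (18 with OncoE6). With about 30 HSIL cases the sensitivity differences will carry half-widths of roughly 12 to 24 points. A two-sided 95% CI may include zero where the one-sided 0.05 test rejects, so the text should say that the interval describes precision and does not replace the test.

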3.3 Number of Study Participants to be Enrolled

3.3.1 Proposed sample size

This study will enroll 300 participants.

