4.3.4 Clinical assessments

Targeted physical exam

This should be documented in the source documents only. A targeted physical examination is to include vital signs (temperature, pulse, and blood pressure) and assessment of Karnofsky Performance Status (KPS) ([Appendix II](#)). The rest of the

targeted exam is to be driven by any previously identified or new signs or symptoms including diagnoses that the participant has experienced since the last visit.

The vulvar and perianal area will be examined for signs of HPV-related lesions. The presence or absence of vulvar/perianal condyloma will be recorded on the CRFs. Anal cytology and digital anal/rectal exam (DARE) are performed at each study visit. HRA with biopsy of visible disease (in the anal canal or perianus) (or at least 2 random sites from 2 different quadrants, if no disease is visible) will be performed to assess anal HPV-associated disease at visits 1, 3, and 5. Exception: If the participant is pregnant at visits 3 or 5, the HRA with biopsy will be deferred.

The participant will have a cervical/vaginal speculum exam with cervical/vaginal cytology (for visit 1, the participant will need a specimen if not available from within the past 42 days) and HPV collected annually beginning with the initial assessment (Visit 1).

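### Section 7.1 states mean follow-up in months where its own figures need years, and section 7.2.1 leaves the HSIL incidence denominator unclear and without a stop at the last HRA

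*Combined protocol and SAP*

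**What the plan says.** Section 7.1 plans the HSIL incidence estimate on the women who are HSIL-negative at the first HRA. It says "If these women are followed for an average of 1.8 months, we would expect" and multiplies 1.8 by 270. It then tabulates 95% Poisson intervals at two underlying rates, 2.06 and 3.09 per 100 person-years, "with 486 person-years of observation".

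Section 7.2.1 estimates the rate as the number of HSIL cases "divided by the cumulative years of follow-up", and closes the sentence with three words that tie this follow-up to the cases. It gives no rule for when a woman's person-time ends.

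HSIL is a biopsy diagnosis (section 7.1). Section 4.3.4 says that HRA with biopsy "will be performed to assess anal HPV-associated disease at visits 1, 3, and 5", that is, at Months 0, 12 and 24. The synopsis adds HRA for abnormal cytology at the interim visits. HRA is deferred if a woman is pregnant at Visit 3 or 5 (4.3.4); she stays on study, and what is omitted is logged as missed (4.3.8). A histologic HSIL diagnosis ends participation (5.1).

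**The concern.** Two things do not fit together.

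First, the stated unit contradicts the product that follows it. This is the only precision statement for the incidence part of primary objective 2.2.3, so its input should be correct.

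Second, the estimator in 7.2.1 can be computed in more than one way. A denominator limited to the cases is not an incidence rate. A denominator of all follow-up includes time in which no event could be recorded: a woman last seen at Month 6 or 18 with normal cytology, or one who attends Visit 3 or 5 without the HRA. That time can only lower the rate. Two analysts following 7.2.1 could report different primary results from the same data.

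**Working it through.** **Inputs.** Enrolment: "This study will enroll 300 participants" (3.3.1). Prevalence: "it is anticipated that approximately 10% of women will have HSIL" (7.1). Baseline-negative women: 300 × 0.90 = 270, as 7.1 uses. Mean follow-up: 1.8, unit in question. Study length: 2 years with 6-monthly visits (1.3).

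**Reproducing the plan's figures.**
- In years: 270 × 1.8 = 486 person-years.
- In months: 270 × 1.8/12 = 40.5 person-years, one twelfth of that.
- Events implied at 486: 0.0206 × 486 ≈ 10 and 0.0309 × 486 ≈ 15.
- Log-scale interval, rate × exp(±1.96/√events):
  - 10 events: 2.06 (1.11, 3.82)
  - 15 events: 3.09 (1.86, 5.12)

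Both rows match the table. Exact Poisson limits, (0.99, 3.78) and (1.73, 5.09), do not. At 40.5 person-years the same rates imply 0.83 and 1.25 events, with log-scale limits of about 0.24 to 17.6 and 0.54 to 17.8. The table was therefore computed on years.

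**Literal reading of 7.2.1.** Suppose 10 cases, all found at the Month 12 or Month 24 HRA. Their own time is between 10 × 1 = 10 and 10 × 2 = 20 person-years, so the rate would be 100 to 50 per 100 person-years, against 10/486 = 2.06 for the cohort. This cannot be the intention, but it is what the sentence says.

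**Cohort reading: time after the last HRA.** The documents give no dropout pattern, so each row below is an assumption chosen to give a mean follow-up of 1.8 years. Visits are at nominal times and only scheduled HRAs count.

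| Assumed losses | Mean years to last HRA | Person-years covered | Uncovered |
|---|---|---|---|
| 20% last seen at Month 12 | 0.8×2 + 0.2×1 = 1.80 | 486 | 0% |
| 4.17% lost before each visit | 0.9583² + 0.9583⁴ = 1.762 | 475.7 | 2% |
| 13.3% last seen at Month 6 | 0.867×2 + 0.133×0 = 1.733 | 468 | 4% |
| Constant hazard 0.107 per year | e^−0.107 + e^−0.215 = 1.705 | 460 | 5% |
| 40% last seen at Month 18 | 0.6×2 + 0.4×1 = 1.60 | 432 | 11% |

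In the last row, 10 cases give 10/486 = 2.06 on all follow-up and 10/432 = 2.31 on covered time; 2.06/2.31 = 0.89, an understatement of 11%.

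Two things lie outside the table. HRAs triggered by interim cytology would reduce the uncovered share. HRAs missed by women who still attend would raise it: a woman who attends Visit 5 without HRA, last examined at Month 12, adds a full uncovered year.

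**Effect on precision.** At 432 person-years and the same two rates, the intervals are (1.07, 3.97) and (1.81, 5.28), little different from the table.

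**The case against.** The strongest reply is that nothing in the planning goes wrong. The product is printed beside the faulty word, the table is headed with 486, and the study lasts two years; no reader would size the study on 40.5 person-years. That stands. A reader might infer from the text that the incidence objective was planned on one twelfth of the needed person-time, but the table rows rule this out.

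A reader might also infer that 486 already contains time after the last HRA and should be reduced, for instance to 460–476. The documents do not support this. They do not say how 1.8 was derived or whether it runs to last contact or to last HRA. Completers end at an HRA visit, women with HSIL leave the study at diagnosis, and an 80%/20% split between Month 24 and Month 12 gives 486 person-years that all end at an HRA. A reduced figure would put an assumed dropout pattern into the protocol.

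Nor does section 8.4 add weight. It reviews missed visits and discontinuations, but the only planning figure it names is the 10% prevalence; it does not cite 1.8 or 486.

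What the reply does not meet is the estimator. Section 7.2.1 has no rule for ending person-time, and its closing words point to the wrong denominator. That the bias may turn out small does not make the rule defined.

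**Conclusion.** The point holds in two limited parts. The unit in 7.1 is a wording error with no numerical consequence. The denominator in 7.2.1 is a real gap in the estimator for a primary objective: taken literally it is not a cohort rate, and taken as cohort follow-up it biases the HSIL rate downward.

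The size of that bias cannot be fixed from the documents. About 0% to 11% covers the dropout patterns tried; it rests on a mean follow-up of 1.8 years, nominal visit times and scheduled HRAs only. It is not a bound, because triggered HRAs would lower it and HRAs missed by attending women would raise it. The correction is worth making because it is nearly free and removes a choice that would otherwise be made after the data are seen.

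**What to change.** - **Section 7.1:** replace months with years as the unit of mean follow-up. Leave 486 and the interval table as they are.
- **Section 7.2.1:** define the HSIL denominator as the person-time of all women HSIL-negative at baseline who have at least one later HRA, running from the baseline HRA to HSIL diagnosis or to the last HRA with biopsy, scheduled or triggered. Delete the three closing words that tie follow-up to the cases. The anal HPV paragraph ends the same way and needs the same deletion; the HRA rule does not apply there, since HPV swabs are scheduled at every visit.

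The cost is slightly less person-time and a marginally wider interval. No procedure or sample size changes. Section 4.6 already has the results of interval work-up entered in the CRF at the next scheduled visit; the one thing to confirm is that the date of each triggered HRA is captured.
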